10.3.2 Analytic Plan for Secondary Objectives

To assess safety and tolerability, all adverse events will be summarized in terms of type, grade, timing and attribution to treatment. All enrolled patients who receive at least one injection of study drug or undergo a study-related procedure will be included in the safety analysis. The highest toxicity grades per patient will be tabulated for AEs and laboratory measurements, and the number and percent of patients reporting AEs will be quantified. Listings will be required for all on-study deaths, SAEs and AEs that lead to withdrawal from study. Narratives for all SAEs and deaths on-study will be required. These summaries will be done by age cohort.

Continuous toxicity monitoring will occur using the method of Ivanova et al.⁵¹ While this method may be used to identify an unacceptable level of toxicity after each patient, only values for every 5 patients will be given here. The following table gives the number of unacceptable toxicities that need to be observed after 5, 10, 15, 20, 25, 30 patients to identify an adverse toxicity rate exceeding 20% with a false positive rate (after each patient) of 2% and a desired probability of early stopping of 5%. Unacceptable toxicity is defined as any toxicity requiring discontinuation of pembrolizumab, as defined in Table 4.1.

Number of patients observed: 5 10 15 20 25 30 Number of observed toxicities: 4 6 8 9 11 12

Response assessment: Anti-tumor activity will be assessed using the LUGANO 2014 Response Criteria (Appendix C). Patients who receive consolidation with pembrolizumab will also have disease assessed by the Immune Response Criteria (Appendix F) as an exploratory assessment. To assess progression free survival

(PFS) and overall survival (OS), Kaplan Meier curves for progression and survival will be calculated for each cohort. The 3-year PFS will be determined from this curve for all patients

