4.3 Toxicity Management & Dose Delays/Modifications

Any patient who receives at least one dose of study therapy will be evaluable for toxicity endpoints. Each patient will be assessed for the development of toxicity according to the timeframe referenced in the Schedule of Events table. Toxicity will be assessed according to the CTCAE (version 4.03)

Dosing interruptions are permitted in the case of medical / surgical events or logistical reasons not related to study therapy (e.g., elective surgery, unrelated medical events, patient vacation, and/or holidays). Subjects should be placed back on study therapy within 3 weeks of the scheduled interruption, unless otherwise discussed with the Pl and approved by DSMC. The reason for interruption should be documented in the appropriate eCRF. Once subjects resume treatment, they will continue with the full number of planned cycles of therapy (i.e. treatments will be delayed not skipped).

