4.6.4 Patient Replacement

Any patient who is registered to the study and then withdrawn without receiving any study treatment may be replaced. Any patient who completes fewer than 2 total cycles of therapy and is withdrawn for any reason except PD or toxicity will still be considered evaluable for toxicity endpoints; however, for the purpose of efficacy endpoints, another patient may be added; if the maximum accrual of 30 is reached without achieving the 26 evaluable necessary for evaluation of efficacy, an increase to the accrual goal may be requested with the approval of the Data and Safety Monitoring Committee (DSMC) at Northwestern University. No follow-up is required for patients that withdrew and did not receive any study treatment.

37

Initial Version date: March 10th, 2017

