6.4.2 Secondary Endpoints

Toxicity Endpoints

The frequency and severity of adverse events by type, severity (grade), timing, and attribution to pembrolizumab will be assessed once per cycle according the NCI-CTCAE version 4.03. All patients who receive at least one dose of pembrolizumab will be evaluable for toxicity endpoints.

Efficacy Endpoints

Response and progression will be evaluated using the LUGANO 2014 Response Criteria⁴⁶.

Patients treated with pembrolizumab consolidation will also have disease assessed by the updated immune response criteria⁴⁷ in addition to LUGANO response criteria as an exploratory assessment.

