10.2 Sample Size and Accrual

This is a Phase II study in which the primary aim will be to determine the complete response rate to up front pembrolizumab. The treatment paradigm of this trial will be considered worthy of further evaluation if at least 40% of patients achieve CR at PET#2 (defined as Deauville 1-3).

The target sample size for the primary response analysis is 26 patients, with 4 additional patients to be accrued to account for dropout, so that the total target sample size is 30 patients in order to increase the CR rate to single agent pembrolizumab from the baseline level of 20% in relapsed/refractory patients, to 40% with a power of 84% at an alpha level of 10%. For the analysis of complete response by PET, a single arm single stage Bayesian design with 26 patients may also be used. Response is defined as a Deauville score of 1-3 after the initial treatment with pembrolizumab alone. The posterior probability of a response rate being greater than 50% will be calculated using a non-informative prior

distribution. With 26 patients, the following table gives this posterior probability for an observed number of responses.

Observed number of responses/26: 11 12 13 14 15 Probability that response rate > 40%: 0.61 0.75 0.86 0.92 0.96

Therefore, to be more than 80% sure that the response rate exceeds 40%, at least 13 of 26 responses would need to be observed in the total population. After PET#3, patients will be analyzed as a total population as well as by age cohort for response rate, PFS, and OS.

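### Section 10.3.2 admits undosed patients to the safety analysis, against the at-least-one-dose rule in 4.3 and 6.4.2, and any who enter can modestly lower adverse-event percentages

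*Combined protocol and SAP*

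**What the plan says.** Three places define who counts for safety.

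- Section 10.3.2: "All enrolled patients who receive at least one injection of study drug or undergo a study-related procedure will be included in the safety analysis". The second limb needs no drug exposure, and the term for the procedure is not defined.
- Section 6.4.2: "All patients who receive at least one dose of pembrolizumab will be evaluable for toxicity endpoints".
- Section 4.3: "Any patient who receives at least one dose of study therapy will be evaluable for toxicity endpoints".

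Section 4.6.4 expects some registered patients to go untreated: "Any patient who is registered to the study and then withdrawn without receiving any study treatment may be replaced". It adds: "No follow-up is required for patients that withdrew and did not receive any study treatment".

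Two outputs in 10.3.2 depend on the denominator. One is the descriptive summary, in which "the number and percent of patients reporting AEs will be quantified", reported by age cohort. The other is continuous toxicity monitoring, meant "to identify an adverse toxicity rate exceeding 20" per cent, with stopping counts of 4, 6, 8, 9, 11 and 12 at 5, 10, 15, 20, 25 and 30 patients. The section does not say whether those patient counts mean dosed patients.

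**The concern.** Sections 4.3 and 6.4.2 use slightly different words, but pembrolizumab is given first to every patient, so they select the same people. Section 10.3.2 is the outlier. It can bring in patients who were registered, had a procedure and were never dosed.

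Such patients have few ways of entering the numerator. Section 4.6.4 requires no follow-up. Section 7.2.1 has pre-treatment adverse events reported only if they lead to exclusion or result from a protocol-specified intervention. Section 7.2.3 does collect serious events from consent onward, so the route is narrow but not closed. For toxicity of the study drugs it is closed. An undosed patient with no recorded event lowers every percentage.

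Safety and tolerability is a secondary objective in section 2.2. Its results should not depend on which section the analyst follows. If the same wide denominator fed the stopping rule, the rule would also become less sensitive.

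**Working it through.** **Inputs.** From 10.3.2: the boundary above, a reference rate of 20%, a per-patient false-positive rate of 2% and an overall early-stopping probability of 5%. From 10.2: total accrual of 30. Assumed: u undosed patients among 30, with u from 1 to 4. The documents give no figure for u. Also assumed, for the monitoring check only: a true unacceptable-toxicity rate of 40%.

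**Step 1: reproduce the plan's boundary.** At each n from 1 to 30, take the smallest k with P(X ≥ k) ≤ c, where X is binomial (n, 0.20). The overall crossing probability comes from an exact patient-by-patient recursion.

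- c = 0.017 gives 4, 6, 8, 9, 11, 12, exactly as stated, with overall crossing of 4.95% at a true 20% rate (stated 5%).
- c = 0.020 taken literally gives 4, 6, 7, 9, 10, 12 and 6.0%.

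The stated 2% is therefore consistent with a rounded 1.7%, and the boundary is sound.

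**Step 2: descriptive percentages.** If the undosed contribute no events, reported rate = true rate × (30 − u)/30.

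- u = 1: 20% × 29/30 = 19.3%
- u = 2: 20% × 28/30 = 18.7%
- u = 3: 20% × 27/30 = 18.0%
- u = 4: 20% × 26/30 = 17.3%

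The relative reduction is u/30, or 3.3% to 13.3%. As a count, 6 patients with an event among 26 treated is 6/26 = 23.1%, but 6/30 = 20.0%.

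**Step 3: monitoring, if undosed patients were counted.** Three quantities are compared at a true 40% rate:

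- *Left out*: the recursion is run over the 30 − u treated patients only.
- *Counted, spread evenly*: the recursion is run over 30 patients with event probability 0.40 × (30 − u)/30. Placing the undosed at random among the 30 gives nearly the same values.
- *Counted, all first*: the u undosed occupy the first positions, which is the worst order.

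| Undosed u | Treated | Left out | Counted, spread evenly | Counted, all first |
|---|---|---|---|---|
| 0 | 30 | 69.5% | – | – |
| 1 | 29 | 68.2% | 64.5% | 62.5% |
| 2 | 28 | 68.2% | 59.2% | 55.3% |
| 4 | 26 | 62.5% | 48.1% | 40.7% |

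The values for 28 and 29 treated agree because the boundary rises from 11 at n = 28 to 12 at n = 29. A trial that has not stopped by 28 has at most 10 events, so it cannot reach 12 at the next patient.

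The loss due to the denominator is the third column minus the fourth: about 4, 9 and 14 points for u = 1, 2 and 4. If the undosed come last, the loss is zero, because the boundary has already been applied to every treated patient.

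**The case against.** **The procedure clause has a purpose.** Section 7.2.1 requires reporting of pre-treatment events caused by a protocol-specified intervention, and the clause lets the safety analysis cover them. That aim stands. A separate listing meets it without putting undosed patients into toxicity percentages.

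**A reader might infer that the safety set becomes everyone enrolled, since all have had screening tests.** The documents do not support going that far. The schedule notes in section 5.0 mark the eligibility PET/CT as standard of care and PET#2, the optional repeat biopsy and the correlative bloods as research. The correlative bloods start at pembrolizumab cycle 1. On a narrow reading of the undefined term, few or no undosed patients would qualify. What stands is that the set is ambiguous and conflicts with two other sections.

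**A reader might take 4 undosed patients as expected.** Section 10.2 plans 30 patients, "with 4 additional patients to be accrued to account for dropout". That allowance covers loss from the 26 evaluable. Section 10.1 requires PET#2 as well as a dose, so it can include dosed patients, who belong in the safety set under either rule. Four is only the top of an illustrative range.

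**A reader might conclude that the chance of stopping falls from 70% to 48%.** That compares 30 treated patients with 26, and part of the fall comes from treating fewer people. The proper comparator for u = 4 is 62.5%. The monitored event is also a toxicity requiring discontinuation of pembrolizumab, which an undosed patient cannot have, and 4.3 and 6.4.2 point to dosed patients. The natural reading of the table may already be right, but 10.3.2 does not say so.

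**Conclusion.** The contradiction is in the current text. As written, 10.3.2 admits patients whom 4.3 and 6.4.2 exclude from toxicity endpoints, and 4.6.4 shows that such patients are foreseen. Any who enter without a recorded event lower the reported percentages.

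The size is modest: 0.7 to 2.7 percentage points on a true 20% rate with 1 to 4 undosed among 30. It is zero if every registered patient is dosed, or if the undosed had no qualifying procedure. The stopping-rule effect (about 4 to 14 points at a true 40% rate with even spread) is conditional on undosed patients being counted and on when they enter, and the documents establish neither. Severity is minor to moderate. The primary endpoint, sample size and futility rule are not affected.

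**What to change.** In 10.3.2, define the safety set for adverse-event rates as all patients who received at least one dose of pembrolizumab, matching 6.4.2. State that the patient counts in the toxicity-monitoring table refer to the same patients. List adverse events from study procedures in undosed patients separately, outside these denominators, so that no reportable event is lost.

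The cost is a sentence or two in 10.3.2 and reported rates that may be slightly less favourable. The boundary values do not change.

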3.1 Inclusion Criteria

- 3.1.1 Patients must have a histologically confirmed diagnosis of classical Hodgkin lymphoma including nodular sclerosis, mixed cellularity, lymphocytic-rich, and lymphocyte depleted subtypes by the 4th edition of the WHO Classification of Tumours of Haematopoietic and Lymphoid Tissues published in 2008 (NLPHL excluded).⁴⁵
- 3.1.2 Patients must have measurable disease by the Lugano Criteria (Appendix C).
- 3.1.3 Patients must have previously untreated disease (except for one week or less of corticosteroids).
- 3.1.4 Patients must be age ≥ 18 years.
- 3.1.5 Patients must exhibit a/an ECOG performance status of 0-1.
- 3.1.6 Stage III and IV patients may any International Prognostic Score (IPS).
- 3.1.7 Stage I and II patients must have at least one NCCN unfavorable risk factor (see Appendix D).
- 3.1.8 Patients must have adequate organ and bone marrow function within 14 days prior to registration, as defined below:

leukocytes ≥ 3,000/mcL
 absolute neutrophil count ≥ 1,500/mcL
 platelets ≥ 100,000/mcl

total bilirubin within normal institutional limits

AST(SGOT)/ALT(SPGT) ≤ 2.5 X institutional upper limit of normal (ULN)

creatinine within normal institutional limits

Platelet transfusions are acceptable prior to treatment to achieve the above numbers, however growth factors are not allowed within 14 days of registration.

3.1.9 Females of child-bearing potential (FOCBP) and males must agree to avoid becoming pregnant, or impregnating a partner, respectively, by complying with any of the approved contraception techniques (see section 4.5.2) prior to registration, for the duration of study participation, and for 120 days following completion of therapy. Abstinence is acceptable if this is the usual lifestyle and preferred contraception for the subject. Should a female patient become pregnant or suspect she is pregnant while participating in this study, she should inform her treating physician immediately.

NOTE: Male patients will be considered of non-reproductive potential if they have azoospermia. Female patients will be considered of non-reproductive potential if they are either:

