⁵ Elderly patients may receive consolidation for a total of up to 1 or 2 years pembrolizumab treatment. Elderly patients who do not achieve CR after additional AVD will have pembrolizumab consolidation for up to 32 additional doses. Elderly patients with Stage III/IV disease who achieve CR after <6 cycles AVD will receive pembrolizumab consolidation for up to 14 additional doses. See section 4.2.3 for details.

⁶ See study schema in 1.2

⁷ Patients will be followed (either by routine clinic visit or by phone call) for survival every 12 weeks (±7 days) for 2 years from the last dose of study drug. Patients should also be monitored for occurrence of an allogeneic stem cell transplant within 24 months from the last study treatment. If patient undergoes an allo-SCT in this timeframe, transplant parameters and adverse events must be reported as specified in section 4.6.3 (up to 18 months from the time of SCT).

⁸ Vital Signs include: Blood pressure, pulse, respiratory rate, and oxygen saturation

⁹ See Appendix A

¹⁰ See Appendix D

¹¹ Comprehensive chemistry panel and CBC with differential are required within 14 days of study registration. Chemistry panel will include glucose, calcium, albumin, ALT, AST, sodium, potassium, total bilirubin, alk phose, and creatinine. CBC with differential must include Absolute Neutrophil Count.

¹² At baseline and every 6 weeks while on therapy with pembrolizumab.

¹³Patients must have HIV Ab screen; and Hepatitis B Sag, Sab, and core; and Hepatitis C Ab testing within 6 weeks of registration.

Trial Period:	Screening Phase	Treatment Cycles ¹						Off Rx	Surveillance			
		Pemb	orolizun	nab		AVD ^{2,3}		AVD ^{3,4}	sment	Pembrolizumab ⁵	Discont	Survival Follow-Up
Treatment Cycle/Title:	Main Study Screening	1	2	3	PET #2	1-2	PET #3	3-66	emo Asses	4-35		
Scheduling Window (Days):	Within 28 days of registration	1 ± 3	22 ± 3	43 ± 3	[64 ± 3	[120 ± 3	Post-Che	2-4 weeks after last dose of chemotherapy ± 3	30 days after last dose (pembro or AVD, ±5 days)	Every 12 weeks

²⁰ Adverse events will be followed for the first 30 days after treatment discontinuation. SAE's will be recorded for 90 days after treatment discontinuation. For patients who undergo allogeneic stem cell transplant (SCT) within 24 months of last study treatment, transplant parameters and adverse events will be recorded according to section 4.6.3 (up to 18 months from the time of SCT).

²¹ Echo or MUGA to be repeated after 4 cycles of doxorubicin

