Recording of AEs should be done in a concise manner using standard, acceptable medical terms. In general, AEs are not procedures or measurements, but should reflect the reason for the procedure or the diagnosis based on the abnormal measurement. Preexisting conditions that worsen in severity or frequency during the study should also be recorded (a preexisting condition that does not worsen is not an AE). Further, a procedure or surgery is not an AE; rather, the event leading to the procedure or surgery is considered an AE.

If a specific medical diagnosis has been made, that diagnosis or syndrome should be recorded as the AE whenever possible. However, a complete description of the signs, symptoms and investigations which led to the diagnosis should be provided. For example, if clinically significant elevations of liver function tests are known to be secondary to hepatitis, "hepatitis" and not "elevated liver function tests" should be recorded. If the cause is not known, the abnormal test or finding should be recorded as an AE, using appropriate medical terminology (e/g/ thrombocytopenia, peripheral edema, QT prolongation).

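### The laboratory safety table takes each patient's highest grade without a baseline reference, so a stable abnormality allowed at entry is tabulated as a toxicity grade

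*Combined protocol and SAP*

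**What the plan says.** Section 10.3.2 of the combined protocol and SAP gives two summary rules for safety. For adverse events, "all adverse events will be summarized in terms of type, grade, timing and attribution to treatment". It then adds that "The highest toxicity grades per patient will be tabulated for AEs and laboratory measurements". Laboratory measurements are named beside AEs, but no baseline grade, shift, worsening rule or time window is given for them. On subgroups it says "These summaries will be done by age cohort".

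Section 3.1.8 sets the laboratory entry limits: "Patients must have adequate organ and bone marrow function within 14 days prior to registration, as defined below". The list covers leukocytes (at least 3,000/mcL), neutrophils (at least 1,500/mcL), platelets (at least 100,000/mcL), AST/ALT (up to 2.5 x ULN), and bilirubin and creatinine (both within institutional normal limits). Haemoglobin and lymphocytes are not listed. It also says "Platelet transfusions are acceptable prior to treatment to achieve the above numbers".

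Section 7.2.1, on recording AEs, states that "a preexisting condition that does not worsen is not an AE".

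Pre-treatment values are available: footnote 11 to the Section 5.0 table says the chemistry panel and "CBC with differential are required within 14 days of study registration".

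**The concern.** Safety and tolerability is the first secondary objective (Section 2.2), and the trial has one arm. No control group shows how much laboratory abnormality these patients carry because of their disease. If the table keeps only the highest grade, a patient who enters with anaemia, or with ALT at twice the upper limit, and stays there is indistinguishable from one who developed the abnormality on treatment.

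Two features add to this. CBC and chemistry are scheduled at pembrolizumab cycle 1, and Section 4.2.1 places dosing after that day's assessments. With no post-baseline window, a sample drawn before any drug can supply the tabulated grade. Also, the summaries are split by age, and only patients aged 60 or over can receive 14 or 32 consolidation doses (Section 4.2.3). The highest grade is then taken over unequal numbers of draws in the two age groups.

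**Working it through.** The plan states no figure for this table, so there is none to reproduce. The check has four parts.

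**1. Which analytes are affected (Section 3.1.8).**

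| Analyte | Entry rule | Can a patient enter abnormal? |
|---|---|---|
| AST/ALT | up to 2.5 x ULN | yes, explicitly |
| Haemoglobin, lymphocytes | none | yes, to any degree within the investigator's judgement |
| Leukocytes, neutrophils, platelets | numeric floor | yes, if the floor lies below the laboratory's normal range; platelets may be raised by transfusion |
| Bilirubin, creatinine | institutional normal | no |

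**2. Does another rule supply the baseline?** The non-worsening rule in Section 7.2.1 concerns what is recorded as an AE. It protects the AE summary. It is not stated for the tabulation of graded laboratory measurements.

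**3. Arithmetic for 30 patients.** Assume a share b enters abnormal and stays stable, and 10% of the others become newly abnormal.

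- Highest-grade table: 30 x [b + (1 - b) x 0.10]
- Worsened-from-baseline count: 30 x (1 - b) x 0.10

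| b | Highest grade | Worsened | Difference (30b) |
|---|---|---|---|
| 10% | 5.7 | 2.7 | 3 |
| 30% | 11.1 | 2.1 | 9 |
| 50% | 16.5 | 1.5 | 15 |

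**4. Haemoglobin illustration, no drug effect.** Assumed: between-patient SD 1.6 g/dL, within-patient SD 0.4, grade boundaries 12, 10 and 8 g/dL, mean 12.5 or 13.5, and 3 or 9 post-baseline draws. The single-value SD is sqrt(1.6² + 0.4²) = 1.649. At baseline, P(grade 1 or worse) = Φ((12 - 12.5)/1.649) = 38% and Φ((12 - 13.5)/1.649) = 18%. P(grade 2 or worse) = Φ((10 - 12.5)/1.649) = 6.5% and Φ((10 - 13.5)/1.649) = 1.7%. The worst post-baseline grades come from simulation.

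| | Mean 12.5 | Mean 13.5 |
|---|---|---|
| Grade 1 or worse at baseline | 38% | 18% |
| Tabulated grade 1 or worse (3 / 9 draws) | 46.1% / 52.2% | 23.8% / 28.8% |
| Worse than own baseline grade | 13.4% / 21.0% | 8.3% / 13.2% |
| Tabulated but not worsened (difference) | 32.7% / 31.2% | 15.5% / 15.6% |
| Tabulated grade 2 or worse | 9.2% / 11.8% | 2.6% / 3.6% |

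Of 30 patients, the tabulated-but-not-worsened group is 30 x 0.327 = 9.8 to 30 x 0.312 = 9.4 at mean 12.5, and 30 x 0.155 = 4.7 at mean 13.5. Grade 3 or worse is 0.07-0.8% across these settings, at most 30 x 0.008 = 0.24 patients.

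**What a baseline reference leaves behind.** The worsened row is pure chance, since no drug effect was simulated. Scheduled draws are 3 + (4 to 6) + 1 = 8-10 for AVD without consolidation, counting the cycle 1 pre-dose draw, and 32 more, 40-42, with the long consolidation. At 40 draws and mean 12.5, 59% are tabulated with some grade and 31% still count as worse than baseline.

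**The case against.** The strongest reply is that the plan is silent rather than wrong. One sentence covers AEs and laboratory measurements, it speaks of toxicity, Section 7.2.1 counts an abnormal laboratory finding as an AE only within its worsening rule, and Section 7.1 follows laboratory values until they return to baseline. An analyst could carry that rule over. This is a fair reading, but the sentence names laboratory measurements as a second item and gives a complete rule for them: the highest grade. Someone following it literally would tabulate stable entry abnormalities.

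Other parts of the reply stand and set the limits of the point:

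- A reader might infer that the plan attributes these laboratory grades to the drugs. It does not. Attribution is specified for AEs, and that summary has its own protection.
- A reader might infer that every laboratory parameter is affected. Bilirubin and creatinine are not.
- A reader might infer that a baseline reference also removes visit-to-visit noise. It does not, as the residual 13-21% and 31% at mean 12.5 show.
- The haemoglobin inputs are assumptions. Zero drug effect is artificial too, since Sections 8.2.10, 8.3.10 and 8.4.9 list marrow effects for all three AVD drugs.

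**Conclusion.** The point holds for AST/ALT, haemoglobin and lymphocytes, and for leukocytes, neutrophils and platelets where the entry floor lies below normal. As written, Section 10.3.2 would show a stable entry abnormality in these analytes as a toxicity grade, and the table would not let a reader separate it from change on treatment.

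The size depends on how many patients enter abnormal, which the documents do not give. Under the assumptions above it is about 5 to 10 of 30 patients for haemoglobin. It lies mainly at grades 1-2, with grade 3 or worse affecting well under one patient.

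A reader might go further and conclude that the trial's safety finding or its decisions are biased. The documents do not support that. The primary endpoint is complete response at PET#2, and the toxicity stopping rule counts events requiring discontinuation of pembrolizumab, not highest laboratory grades. This is an inexpensive improvement to a descriptive secondary table.

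**What to change.** In Section 10.3.2, replace the laboratory part of the sentence with wording such as:

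> For each laboratory parameter, baseline grade (last value before the first pembrolizumab dose) will be cross-tabulated against worst post-baseline grade, separately for induction, AVD and consolidation. The number of patients whose grade worsened from baseline will be reported, with grades 3-4 shown separately.

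Add one sentence saying that worsening by a single low grade will not be described as drug toxicity, because repeated draws cross grade boundaries by chance. Reporting by phase also keeps the long consolidation schedule from inflating the older group's table as a whole.

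The cost is SAP wording and a somewhat longer table. Baseline CBC and chemistry are already required, so no visits, samples or patients are added, and the worst-grade totals remain visible as the margin of the shift table.
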